#### 5.2 Secondary Objectives

To determine the pharmacokinetics at each dosing level of SPI-1005.

## **6** STUDY DESIGN

#### 6.1 Overview

This clinical trial is a phase 2b, randomized, double-blind, placebo-controlled study to evaluate the safety and efficacy of SPI-1005 in Meniere's disease. The study is planned to be conducted in adult volunteers with Meniere's Disease (probable or definitive diagnosis) with active symptoms in the months preceding study enrollment. Study participants will be randomized into three dosing arms: SPI-1005 200 mg/BID, SPI-1005 400 mg/BID, or placebo (1:1:1). This double-blind study will evaluate both safety and efficacy of the investigational treatment.

Participants aged 18-75 years, with probable or definitive Meniere's disease will undergo baseline testing to assess severity of sensorineural hearing loss, tinnitus and vertigo. This is a multicenter study that includes patients from approximately 12 US sites.

During the study, and 28 days after completion of treatment, participants will be evaluated for safety (adverse events, physical examinations, vital signs and clinical laboratory testing (CBC, serum chemistry). Trough plasma levels of ebselen and its major metabolite (2-glucuronyl selenobenzanilide) will be evaluated using liquid chromatography-mass spectrometry (LCMS) at specified visits. Additionally, plasma will be analyzed for selenium at the corresponding visits. Female participants will receive pregnancy testing at visit 1, and those found to be pregnant will be excluded from the study and monitored for adverse events.

The effect of SPI-1005 on hearing and balance will be evaluated. Hearing will be evaluated at baseline, at the end of 28 days of study treatment, and 28 days after completing study treatment. Tinnitus and vertigo will be evaluated with the Tinnitus Functional Index (TFI) and the Vertigo Symptoms Scale (VSS), respectively. These tests will be administered at baseline, on days 14 and 28

This document is confidential and proprietary to Sponsor and EA and for restricted circulation and access only. No part of it may be transmitted, reproduced, published or used by any person/s without prior written authorization.

Version No.: Final 1.0

Page 10 of 38

Sponsor Study No: SPI-1005-251

Sponsor Name: Sound Pharmaceuticals, Inc.

NLS Study Code: SPI-1005-251

Short Title of Study: SPI-1005-251 (Sound Pharmaceuticals, Inc)

of treatment, and 28 days after treatment. Hearing thresholds (HL) will be determined using puretone audiometric (air conduction) testing at 250, 500, 1000, 2000, 3000, 4000, 6000, and 8000 Hz, bilaterally. In addition, bone conduction testing with masking will be conducted if the air conduction threshold is >15 dBHL at 250, 500, 1000, 2000, or 4000 Hz. Bone conduction testing will only be performed at screening and in the affected ear (>15 dBHL). A word recognition test using the Wordsin-Noise Test (WINT) at 24, 20, 16, 12, 8, 4, and 0 Signal-to-Noise ratio (SNR) will be used to evaluate hearing.

Following completion of informed consent process and baseline assessments, the study participants will be evaluated by the investigator for enrollment eligibility. Participants that meet enrollment criteria will be randomized and assigned a Subject Identification Code from the list of Subject Identification Codes. The Subject Identification Code must be carefully matched to the study drug before the study drug is dispensed at Clinic Visits 1, and 2.

A general diagram of the study design is provided in Figure 1.

This document is confidential and proprietary to Sponsor and EA and for restricted circulation and access only. No part of it may be transmitted, reproduced, published or used by any person/s without prior written authorization.

Version No.: Final 1.0

Page 11 of 38

A ECRON ACUNOVA

Sponsor Study No: SPI-1005-251

Sponsor Name: Sound Pharmaceuticals, Inc.

NLS Study Code: SPI-1005-251 Short Title of Study: SPI-1005-251 (Sound Pharmaceuticals, Inc) Screen for Screen participants (n=168 estimate) by inclusion and exclusion criteria Eligibility including history and review of systems Estimated Excluded (n=48) Did not meet I/E criteria (n=25) Declined to participate (n=13) Other reasons (n=10) Clinic Visit 1 Informed consent process, perform baseline assessments, confirm Day -28 to 1 eligibility, randomize, complete enrollment by providing study drug. Clinic Visit 2 Day 14 Perform protocol required assessments. Day 28 Clinic Visit 3 Perform protocol required assessments. Day 56 Clinic Visit 4 Final Assessments

#### 6.2 Parameters

All parameters through which the study objectives will be carried out, should be listed. Exact computations will be declared in section 7.8 Definitions and Derived Variables.

#### 6.2.1 Primary Parameter

- Efficacy of SPI-1005 will be determined by the following clinically significant methods and measures (responder analysis):
- ➤ Pure-tone audiometry assessment (250, 500 or 1000 Hz): Improvements from baseline of ≥10 dB at 1 frequency
- ▶ Words-in-Noise Test assessment (0-35): Improvements from baseline of  $\geq 10\%$ 
  - Tinnitus Functional Index (TFI) (0-100) ≥ 10 pt. reduction from baseline

#### **Confidentiality Statement**

Version No.: Final 1.0

A ECRON ACUNOVA

Sponsor Study No: SPI-1005-251

Sponsor Name: Sound Pharmaceuticals, Inc.

| NLS Study Code: SPI -1005 -251 | Short Title of Study: SPI-1005-251 (Sound Pharmaceuticals, Inc) |
|--------------------------------|---|
|                                |   |

- Tinnitus Loudness: Q#2 of TFI  $(0-10) \ge 2$  pt. reduction from baseline
- Vertigo Symptom Scale  $(0-60) \ge 6$  pt. reduction from baseline

Page 12 of 38

#### 6.2.2 Secondary Parameters

Pharmacokinetics parameters will be analyzed for the following parameters:

- 1.  $AUC_{0-t} (mg_h/L)$
- 2.  $C_{max}$  (mg/L)

#### 6.2.3 Safety Parameters

- > Safety of SPI-1005 treatment in adults with Meniere's disease will be analysed using:
  - Physical examinations
  - Vital signs
  - Adverse events
  - Hematology (CBC)
  - Serum chemistries.

#### 6.2.4 Exploratory Parameters

- Secondary pure-tone audiometry assessments (250, 500 or 1000 Hz): Improvements from baseline of ≥10 dB at 2 adjacent frequencies or ≥20 dB at 1 frequency
- Secondary Words-in-Noise Test assessments (0-35): Improvements from baseline of ≥20% or ≥4 words

## 7 GENERAL STATISTICAL CONSIDERATIONS

#### 7.1 Descriptive Statistics

The following descriptive statistics will be calculated for continuously distributed data:

- n
- Mean
- Standard Deviation (also denoted as SD)
- Minimum (also denoted as Min)
- Median
- Maximum (also denoted as Max)
- Inter Quartile Range (IQR)

#### **Confidentiality Statement**

Statistical Analysis Plan Version No.: Final 1.0

Page 13 of 38

Sponsor Name: Sound Pharmaceuticals, Inc.

Sponsor Study No: SPI-1005-251

CRON ACUNOVA

| NLS Study Code: SPI-1005-251 | Short Title of Study: SPI-1005-251 (Sound Pharmaceuticals, Inc) |
|------------------------------|---|
|                              |   |

For categorical variables, counts and percentages will be calculated.

For continuous variables, the decimal places for n, minimum and maximum will be provided as per the reported value. Decimal places for mean, Q1, Q3 and median will be reported one decimal place more than the reported value. The decimal place for standard deviation will be reported two decimal places more than the reported value.

In all statistical tables, p-values will be reported as specified by the statistical program used, at least up to three decimal places. P-values less than 0.001 will be reported as provided by SAS®, Version 9.2 or higher (e.g. '<0.0001'). All tests will be two-sided at the  $\alpha = 0.05$  level of significance, if not stated otherwise.

In by-visit summary tables only scheduled visits will be presented. All visits (both scheduled and unscheduled) will be presented in listings.

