#### 7.8 Definitions and Derived Variables

For the statistical analysis, two different doses and placebo will be denoted according to the following table.

| Treatment             | Label           |
|-----------------------|-----------------|
| SPI-1005 po BID 200mg | SPI-1005 200 mg |
| SPI-1005 po BID 400mg | SPI-1005 400 mg |
| Placebo po BID        | Placebo         |

In the following table, the definitions and calculation of derived variables are summarised.

| Variable / Term | Definition / Way of calculation   |  |
|-----------------|---|--|
| Baseline        | The last assessment on or before to the treatment start date. The most recent measurement prior to treatment start regardless of whether the measurement is collected at a scheduled or unscheduled visit will be considered for the baseline.  |  |
| End of study    | The date on which the last patient completes the last visit (includes follow-
up visit).   |  |
| BMI             | Weight in kg / Height in m    |  |
| Treatment Start | 
 
The earliest date of 'date of drug dispense' (Date of dispensing) from Study
 
Drug Dispensing and Drug Accountability eCRF form, where the patient has:
 
Answered 'Yes' to question, Study medication dispensed? And,
 
Recorded at least one capsule used for the question, 'Number of capsules taken'
 
If the drug administration date is unavailable and only the last dose date of the patient is available, then the Randomization date will be considered as the treatment start date.
 
 |  |

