#### 8.4.2 Clinical Laboratory Evaluations

Blood samples for clinical safety laboratory assessments will be collected at the following time Visit 1, Visit 2, Visit 3 and Visit 4. The following parameters will be analyzed under these categories:

| Hematology  | Chem                 | nistry               |
|-------------|----------------------|----------------------|
| RBC         | Sodium               | Albumin              |
| Hematocrit  | Potassium            | AST (SGOT)           |
| Hemoglobin  | Chloride             | ALT (SGPT)           |
| Platelets   | Bicarbonate          | GGT                  |
| WBC         | Glucose              | Total bilirubin      |
| Noutrophile | Blood urea nitrogen  | Alkaline phosphatase |
| Neutrophils | (BUN) or Urea        |                      |
| Lymphocytes | Creatinine           | Uric acid            |
| Monocytes   | Calcium              | LDH                  |
| Basophils   | Magnesium            | Cholesterol          |
| Eosinophils | Inorganic phosphorus | Triglycerides        |
|             | Total protein        |                      |

Laboratory results will be summarized descriptively for actual and change from baseline values by visits and treatment for each category of clinical chemistry and hematology. In addition, baseline shift tables will be presented for the lab parameters by visits and treatments for laboratory categories, the results falling out of normal ranges will be classified as Normal, Abnormal High and Abnormal Low and will be used for the shift tables. The 'Normal', 'Abnormal Low' and 'Abnormal High' values are determined based on the laboratory normal ranges. The number and percentage of patients reaching 'Normal', 'Abnormal CS' and 'Abnormal NCS' results for laboratory parameters will be summarized All laboratory results will be listed in data listings, the abnormal values will be flagged in the listings.

This document is confidential and proprietary to Sponsor and EA and for restricted circulation and access only. No part of it may be transmitted, reproduced, published or used by any person/s without prior written authorization.

Version No.: Final 1.0

E ECRON ACUNOVA

Sponsor Study No: SPI-1005-251

Sponsor Name: Sound Pharmaceuticals, Inc.

NLS Study Code: SPI-1005-251 Short Title of Study

Short Title of Study: SPI-1005-251 (Sound Pharmaceuticals, Inc)

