#### **Confidentiality Statement**

ECRON ACUNOVA

Sponsor Study No: SPI-1005-251

Version No.: Final 1.0

NLS Study Code: SPI-1005-251

Page 35 of 38

Sponsor Name: Sound Pharmaceuticals, Inc.

Short Title of Study: SPI-1005-251 (Sound Pharmaceuticals, Inc)

| Table No.      | Table  |
|----------------|--|
| TADI = 14.2.11 |  |
| 1ADLE 14.3.11  | Summary of Shift from Baseline of Vital Signs by Visit: Categorical      |
|                | Variable (Safety Population)   |
| TABLE 14.3.12  | Summary and Change from Baseline of Lab parameters(Hematology) by        |
|                | Visit and Treatment (Safety Population)                                  |
| TABLE 14.3.13  | Summary and Change from Baseline Lab Parameters (Clinical Chemistry)     |
|                | by Visit and Treatment (Safety Population)                               |
| TABLE 14.3.14  | Summary of Shift from Baseline of Lab Parameter (Hemotology) Results     |
|                | Based on the Refernce Range by Visit and Treatment: Categorical Variable |
|                | (Safety Population)  |
| TABLE 14.3.15  | Summary of Shift from Baseline of Lab Parameter (Hemotology) Results     |
|                | Based on the Refernce Range by Visit and Treatment: Categorical Variable |
|                | (Safety Population)  |
| TABLE 14.3.16  | Summary of Lab Parameters (Urine Pregnancy) (Point of care testing) by   |
|                | Treatment (Safety Population)  |

This document is confidential and proprietary to Sponsor and EA and for restricted circulation and access only. No part of it may be transmitted, reproduced, published or used by any person/s without prior written authorization. 37

Statistical Analysis Plan Version No.: Final 1.0

Page 36 of 38

EX ECRON ACUNOVA

Sponsor Study No: SPI-1005-251 Sponsor Name: Sound Pharmaceuticals, Inc.

 NLS Study Code: SPI -1005 -251
 Short Title of Study: SPI -1005 -251 (Sound Pharmaceuticals, Inc)

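### Laboratory results from unscheduled post-baseline draws are listed but not counted by arm in the haematology and chemistry tables, and no table shows each patient's worst value

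*SAP*

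**What the plan says.** **Which visits are tabulated.** SAP 7.1: "In by-visit summary tables only scheduled visits will be presented". It continues: "All visits (both scheduled and unscheduled) will be presented in listings".

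**Baseline.** SAP 7.8 is more inclusive before dosing. Baseline is "The most recent measurement prior to treatment start regardless of whether the measurement is collected at a scheduled or unscheduled visit".

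**Laboratory plan.** SAP 8.4.2 sets four draws: "Blood samples for clinical safety laboratory assessments will be collected at the following time Visit 1, Visit 2, Visit 3 and Visit 4". It then plans four outputs:
- Descriptive tables: "Laboratory results will be summarized descriptively for actual and change from baseline values by visits and treatment for each category of clinical chemistry and hematology".
- Shift tables: "baseline shift tables will be presented for the lab parameters by visits and treatments for laboratory categories".
- Counts of Normal, Abnormal CS and Abnormal NCS: "results for laboratory parameters will be summarized", with no mention of visits.
- A listing of every result, with abnormal values flagged.

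**Table list.** SAP Section 13 lists a haematology summary (14.3.12), a clinical chemistry summary (14.3.13) and two shift tables (14.3.14 and 14.3.15). All four are by visit and treatment. Both shift tables begin "Summary of Shift from Baseline of Lab Parameter (Hemotology) Results". The list contains no worst-value laboratory table and no laboratory clinical-significance table.

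**Standing of these outputs.** Safety is a primary objective (SAP 5.1), and haematology and serum chemistry are two of the five safety parameters in SAP 6.2.3. The protocol synopsis says laboratory results will be summarised by group and compared. SAP Section 4 describes the table specifications as guidance for producing the output.

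**The concern.** Unscheduled draws are not a random sample of a patient's results. Repeat draws, and draws taken when a patient stops early, are often prompted by an abnormality. A rule that tabulates scheduled visits only can therefore set aside the results most likely to be abnormal. The effect is also one-sided: an unscheduled value may enter the tables as a baseline, but an unscheduled value after dosing may not.

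A listing preserves the individual value but gives no count by arm. The protocol promises a comparison between groups, and for these results a reader would have to build it by hand. If several such values fell in one arm, the laboratory tables could look cleaner than the data.

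A separate inconsistency makes the same tables harder to rely on. Section 13 does not list two outputs that 8.4.2 plans: a chemistry shift table and the laboratory clinical-significance counts.

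**Working it through.** The plan gives no figure to reproduce here, and no power or error-rate calculation applies. The check sets the sections side by side, with simple counts.

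1. **Does the rule reach the laboratory tables?** SAP 7.1 governs by-visit summaries. SAP 8.4.2 and Section 13 make 14.3.12 to 14.3.15 by visit. So all four take scheduled results only, apart from the baseline value, which 7.8 allows to be unscheduled.

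2. **How often is a patient sampled on schedule?** The protocol's schedule of assessments gives one baseline visit and three later ones, on Days 14, 28 and 56, each with a window of 3 days either side. Two of the three fall in the 28-day treatment period. The nominal gaps between post-baseline draws are 28 − 14 = 14 days and 56 − 28 = 28 days. The schedule has no early-termination column, and the SAP gives no rule for assigning a repeat or early-termination draw to a visit.

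3. **Is there a table that is not by visit and would catch the rest?** The only candidate is the clinical-significance summary in 8.4.2, which carries no visit qualifier; the matching vital-sign summary in 8.4.3 is by visit. Section 13 lists a categorical table for vital signs (14.3.10) and a physical examination summary (14.3.8), but no laboratory equivalent. No listed table takes each patient's highest or lowest post-baseline value.

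4. **What happens to one patient?** Take a hypothetical patient with normal ALT on Day 14 and a raised ALT on an unscheduled Day 20 draw, who then leaves the study. SAP 7.5.1 applies no imputation. In 14.3.13 the patient contributes a normal value at Visit 2 and is missing at Visits 3 and 4. The raised value appears only in the flagged listing.

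5. **Size per patient.** SAP 7.6 plans 40 per arm, so one such patient is 1/40 = 2.5% of the arm.

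6. **Reach of the repeated title.** The 8.4.2 table names 10 haematology analytes and 11 + 10 = 21 chemistry analytes, 31 in all. Both listed laboratory shift tables are haematology. Read literally, Section 13 therefore gives a shift table to 0 of the 21 chemistry analytes, which include AST, ALT, GGT, total bilirubin, alkaline phosphatase and creatinine. SAP 8.4.2 plans shifts without that restriction.

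**The case against.** The case for leaving the plan alone is fair in several respects.

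- Showing only scheduled visits is an ordinary convention for by-visit tables, and it keeps the denominators at each visit interpretable.
- Nothing is lost from the record: every result is listed and abnormal values are flagged.
- SAP 7.1 makes the maximum a standard statistic, so peaks at scheduled visits appear in 14.3.13 by visit and arm. The shift categories have no scale, but at those visits worsening from an already high baseline still enters the change-from-baseline summary.
- Adverse event tables are not limited to scheduled visits, so toxicity reported as an adverse event, including one that stops treatment, is counted there.
- Only a synopsis and schedule of the protocol are available, so the full text may deal with early-termination samples.

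All of this stands, and it limits the point to unscheduled post-baseline results and each patient's own worst value. It does not remove the point. A per-visit maximum shows one extreme value per arm, not how many patients had one. An adverse event count depends on the event being reported, and it does not carry the laboratory value.

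A reader might infer three stronger things that the documents do not support:

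- That every unscheduled result is excluded. Unscheduled values can serve as baseline and are all listed, and the 8.4.2 clinical-significance summary is not restricted by visit.
- That all chemistry shifts are missing from the plan. SAP 8.4.2 plans shifts for the laboratory categories, 14.3.12 and 14.3.13 form a haematology and chemistry pair, and Section 4 treats the table list as guidance. The repeated title is probably a clerical slip.
- That the patient in the example would be tabulated as normal throughout. Without imputation, the patient is normal at Visit 2 and missing afterwards.

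**Conclusion.** The point holds as an inexpensive improvement to a primary safety output. It is not evidence that the plan conceals laboratory harm. As written, a post-baseline abnormality found only on an unscheduled draw is absent from the haematology and chemistry summary and shift tables, and no listed table gives a per-patient worst value.

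Each affected patient is 2.5% of an arm, assuming the planned 40 per arm are in the safety population. The documents give no rate of unscheduled draws, so the total effect cannot be estimated; it is nil if there are none. The conclusion also assumes that unscheduled and early-termination results are not mapped to a scheduled visit by a rule outside the available text.

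The mismatch between Section 13 and 8.4.2 is real, but it is a matter of reconciling the two. It would be minor on its own.

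**What to change.** 1. Keep the scheduled-visit rule in 7.1 for mean-by-visit summaries.
2. Add to Tables 14.3.12 to 14.3.15 a worst post-baseline row for each analyte. Define it as each patient's highest and lowest value over all scheduled and unscheduled post-baseline results, including any collected at early termination. In the shift tables, cross the baseline category with the worst category.
3. Optionally, show that row for the liver and renal analytes as multiples of the upper reference limit. The plan does not promise this, but it gives the shift categories a scale.
4. Reconcile Section 13 with 8.4.2: make 14.3.15 the clinical chemistry shift table, and list the laboratory Normal / Abnormal CS / Abnormal NCS table.

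Vital-sign shift Table 14.3.11 needs no change. It shifts an overall categorical interpretation, so it has no highest or lowest value to add.

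**Cost.** A short SAP amendment, best made before unblinding, with one extra row per analyte, one corrected title and one added table. No new data are needed. The downside is that a worst-value row shows more abnormal results in every arm, including some that arise by chance, so it should be read against placebo.

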#### 7.2 Randomization and Blinding Process

This study is a randomized, double-blind, placebo-controlled study design. Patients will be randomized to treatment, either placebo or two different doses of SPI-1005 (1:1:1). Study center and sponsor personnel involved in the conduct and interpretation of the study will not have access to treatment codes. Laboratory personnel, and contracted designees of SPI who statistically analyze the data, will be blinded to the study treatment received by each study participant. The bioanalytical staff analyzing PK samples will be provided a copy of the random codes but will not report unblinded data until after database lock. The sponsor's medical monitor will receive each

Apart from this, the data management and biostatistics team will be blinded until the database closure. The lead statistician will receive a copy of the unblinded treatment group after the database lock upon receiving a written authorization from the head of Biometrics/Statistics Lead from Sound Pharma to unblind the study.

treatment code in individual envelopes for use in emergency unblinding.

This document is confidential and proprietary to Sponsor and EA and for restricted circulation and access only. No part of it may be transmitted, reproduced, published or used by any person/s without prior written authorization.

Version No.: Final 1.0

Page 14 of 38

Sponsor Study No: SPI-1005-251

ECRON ACUNOVA

Sponsor Name: Sound Pharmaceuticals, Inc.

NLS Study Code: SPI -1005 -251 Short Title of Stud

Short Title of Study: SPI-1005-251 (Sound Pharmaceuticals, Inc)

